9.2.2 Urinalysis

Urinalysis is assessed using dipsticks at Visit 8, Visit 10, Visit 12, and Visit 14 (end of treatment).

Urinalysis results will be listed only.

9.2.3 Pregnancy Test

Serum pregnancy test results will be summarized by visit.

9.3 Vital Signs, Other Physical Findings and Other Safety Data

9.3.1 Vital Signs

Vital signs (systolic blood pressure, diastolic blood pressure and pulse rate) are measured at Visit 1, Visit 4, Visit 5, Visit 6, Visit 7, Visit 8, Visit 9, Visit 10, Visit 12, Visit 14 (end of treatment) and Visit 15 (end of taper).

Summaries will be presented for each vital sign parameter at each visit. Change from baseline (RCT and OLE baseline) to each post-baseline visit will also be presented.

A separate table will be produced, by visit, presenting the incidence of patients with vital signs indicative of a medical condition at Visit 1 and indicative of an AE after Visit 1.

Based on the criteria presented in [Appendix 3](#), potentially clinically significant changes from baseline (RCT and OLE baseline) in vital signs measurements and other defined flagged values will be identified at each visit. The number of patients with a potentially clinically significant change from baseline will be summarized by parameter, and visit. The number of patients with at least one post-baseline flagged vital sign parameter value will be summarized by parameter, and flagged criteria.

9.3.2 Electrocardiogram

An ECG will be performed at Visit 1, Visit 4, Visit 6, Visit 8, Visit 10, Visit 12 and Visit 14 (end of treatment).

Summaries will be presented for mean heart rate, RR interval, PR interval, QRS duration, QT interval, QTcB and QTcF, at each visit. Change from baseline (RCT and OLE baseline) to each post-baseline visit will also be presented.

A separate table will be produced, by visit, presenting the incidence of patients

Based on the criteria presented in [Appendix 3](#), defined flagged values will be identified at each visit. The number of patients with at least one post-baseline flagged ECG parameter value will be summarized by parameter, and flagged criteria.

9.3.3 Physical Examination

A physical examination which includes body weight measurements will be performed at Visit 1, Visit 4, Visit 6, Visit 8, Visit 9, Visit 10, Visit 12, and Visit 14 (end of treatment). Height will be collected as part of the physical examination at Visit 8, Visit 10, Visit 12, Visit 14 (end of treatment).

Any relevant findings at screening are included as part of the patient's medical history. Any changes seen after screening that are indicative of an AE are to be recorded as such on the AE form and included as part of the AE summaries.

Weight along with weight change and height data will be summarized by visit where applicable.

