2.2.2 Safety Endpoints

The long-term safety profile of GWP42003-P will be assessed by evaluating changes in the following, relative to the prerandomization baseline of the GWND18064 lead-in trial:

- Adverse Events (AEs).

- Clinical laboratory parameters.
- Vital signs.
- Physical examination procedures.
- 12-lead electrocardiogram (ECG).
- Effects on menstruation cycles.
- Suicidality.
- Change in growth and development by measurement of height, weight, serum insulin-like growth factor-1 (IGF-1) levels and Tanner Staging (for patients aged ≥ 7 years, or earlier if clinically indicated by onset of menarche or other signs of precocious puberty).

The same analyses will be performed compared to OLE baseline.

3. Overall Study Design and Plan

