9.3.5 Growth and Development

IGF-1 levels will be analyzed as part of the clinical laboratory testing. IGF-1 levels will be summarized on a continuous scale, including change from baseline.

Change from baseline (RCT and OLE baseline) to the end of treatment visit for IGF-1 levels will also be plotted against the Tanner Stages, weight, and height recorded at baseline.

The pubic hair growth (both sexes), genital (males only) and breast (females only) development of all adolescent patients (i.e., ≥ 7 years of age at the time of signing the informed consent form, or earlier if clinically indicated by onset of menarche or other signs of precocious puberty) will be assessed using Tanner Staging. The assessment can either be performed by examination during the study visit or the appropriate Tanner Stage can be indicated by the caregiver, with reference to the chart provided.

Patients will be examined at Visit 8, Visit 10 and Visit 14 (end of treatment). Once a patient

reaches a score of V (i.e., 5) the examination need not be performed again.

Tanner Stages will be summarized on a categorical scale by Visit. Shift table will be created to display shifts from baseline.

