APPENDIX 2 Adverse Events of Special Interest – Abuse Liability based on preferred term

Withdrawal	
 Drug withdrawal convulsions Drug withdrawal headache Drug withdrawal maintenance therapy Drug withdrawal syndrome Drug withdrawal syndrome neonatal Drug rehabilitation Rebound effect Steroid withdrawal syndrome Withdrawal arrhythmia Withdrawal syndrome
Drug abuse and dependence	
 Dopamine dysregulation syndrome Drug abuse Drug abuser Drug dependence Drug dependence, antepartum Drug dependence, postpartum Intentional drug misuse Intentional overdose Maternal use of illicit drugs Neonatal complications of substance abuse Polysubstance dependence Substance abuse Substance abuser Accidental overdose Dependence Disturbance in social behaviour Drug administered at inappropriate site Drug detoxification Drug diversion Drug level above therapeutic Drug level increased Drug screen Drug screen positive Drug tolerance Drug tolerance decreased Drug tolerance increased Medication overuse headache Narcotic bowel syndrome Needle track marks Overdose Prescribed overdose Prescription form tampering Substance use Substance-induced mood disorder Substance-induced psychotic disorder Toxicity to various agents

APPENDIX 3 Ranges for Clinically Significant Changes and Other Defined Flagged Values in Vital Signs

The range of values that will be used to identify clinically significant changes in vital signs parameters (See [Section 9.3.1](#)) are presented in [Table 7](#).

Table 7 Ranges for Potentially Clinically Significant Changes in Vital Signs

Vital Sign	Range
Sitting Systolic BP (mmHg)	Change: < -20, > 20
Sitting Diastolic BP (mmHg)	Change: < -10, > 10
Pulse Rate (bpm)	Change: < -10, > 10
Weight (kg)	Percent Change: $\leq -7, \geq 7$

Defined flagged values that will be used to identify low or high vital signs parameters (See [Section 9.3.1](#)) are presented in [Table 8](#).

Table 8 Other Defined Flagged Values for Vital Signs

Vital Sign	Flag
Sitting Systolic BP (mmHg)	< 90, > 140, > 160
Sitting Diastolic BP (mmHg)	< 50, > 90, > 100
Pulse Rate (bpm)	< 60, > 100
Temperature (°C)	> 38.0, < 36.0
Respiratory Rate (breaths/min)	< 12, > 20

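### Height and weight are part of the primary safety endpoint but are summarised without reference to age or sex, so growth slower than expected for age would not show

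*SAP*

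**What the plan says.** Protocol V2 (4.1.1 and 13.6.2) puts growth in the primary safety endpoint. SAP 2.2.2 lists it as "Change in growth and development by measurement of height, weight, serum insulin-like growth factor-1 (IGF-1) levels and Tanner Staging", assessed as change from the RCT baseline and again from the OLE baseline.

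For analysis, SAP 9.3.3 says: "Weight along with weight change and height data will be summarized by visit where applicable". Height is scheduled at Visits 8, 10, 12 and 14, so first at Day 197. On clinical findings, the same section says "Any changes seen after screening that are indicative of an AE are to be recorded as such on the AE form".

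SAP 9.3.5, the section on growth and development, analyses IGF-1 and Tanner stage. Height and weight enter it only as baseline values: IGF-1 change is "plotted against the Tanner Stages, weight, and height recorded at baseline".

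SAP Appendix 3, Table 7 flags a weight change of 7% or more in either direction. SAP 9.3.1 applies that appendix: "The number of patients with a potentially clinically significant change from baseline will be summarized by parameter, and visit". Weight is in Table 7, although 9.3.1's own list of vital signs names only blood pressure and pulse.

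**The concern.** In a paediatric safety study, the growth question is whether patients gain less height or weight than expected for their age. A change in kilograms or centimetres does not answer it without a reference. The trial supplies none: everyone is on active drug in the extension, and by-visit means and medians (SAP 4.1) combine patients who were 2 to 18 years old at lead-in entry (SAP 3.3). If the plan is followed exactly, a primary safety component has no display that can show its main adverse direction. The one numerical alert for weight also mixes ordinary growth with excess gain.

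**Working it through.** **1. Every planned use of height and weight.**

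| Place | What is planned | Age or sex reference |
|---|---|---|
| SAP 9.3.3 | Weight, weight change and height by visit | None |
| SAP 9.3.5 | Baseline height and weight as plot axes for IGF-1 change | None |
| SAP Appendix 3, Table 7, through 9.3.1 | Weight change of at least 7% up or down | None; same at all ages |
| Protocol V2 13.6.2.3 | Physical examination summarised; height and weight not named | None |
| SAP 7.3 | Age groups 2-5, 6-12 and 13-19 | Demographics only |

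Neither document contains a height- or weight-for-age z-score, percentile, growth velocity or growth chart. Population norms are used, but only to score the SF-36 and CHQ-PF50 (SAP 8.5.1 and Appendix 5).

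**2. Partial slowing.** If the expected gain over an interval is G and a patient achieves a fraction f of it, the observed change is f × G, which is positive for any f above 0. The shortfall (1 − f) × G appears in no display.

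An illustration over Day 1 to Day 729, which is (729 − 1)/365.25 = 1.993 years, follows. The growth figures are assumptions, not from the documents.
- Height, assumed gain 4 to 7 cm a year: half-rate growth still adds 0.5 × 4 × 1.993 = 4.0 cm to 0.5 × 7 × 1.993 = 7.0 cm. With an assumed SD for age of 4 to 7 cm, the z-score falls by 4.0/7 = 0.57 to 7.0/4 = 1.74.
- Weight, assumed gain 1.5 to 4 kg a year from a baseline of 10 to 40 kg: half-rate growth gives 0.5 × 1.5 × 1.993/40 = 3.7% to 0.5 × 4 × 1.993/10 = 39.9%. Such a patient is either unflagged or flagged as a gain.

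**3. Zero gain.** This is a 0% change, inside the band from −7% to +7%, so there is no flag against that baseline. The lower side fires only on an actual loss of at least 7%. A patient who had already gained 7% since RCT baseline and then stalls stays flagged against RCT baseline, but as a gain.

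**4. Ordinary growth and the upper flag.** The steady annual gain that reaches +7% is r = 1.07^(1/y) − 1. From OLE Day 1, y = (Day − 1)/365.25. From RCT baseline, y = (Day − 1 + 7w)/365.25, where w is the number of weeks from RCT baseline to OLE Day 1. The documents do not give w; 12 to 36 is assumed.

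| Visit day | y from OLE Day 1 | r from OLE Day 1 | r from RCT baseline, w = 12 to 36 |
|---|---|---|---|
| 197 | 0.537 | 13.4% | 9.2% to 5.7% |
| 365 | 0.997 | 7.0% | 5.7% to 4.1% |
| 729 | 1.993 | 3.5% | 3.1% to 2.6% |

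The longer the time since baseline, the slower the growth that counts as potentially clinically significant.

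**5. Which baseline is available.** SAP 6.1.2 takes the OLE baseline from Visit 1. Visit 1 weight is required only when entry is more than 28 days after RCT Visit 9 (SAP Table 1, note f), while same-day entry is recommended (SAP 3.1). Visit 1 height is added only for annex patients enrolling after RCT Visit 11 (Annex 1 Version 2, 3.2.1). For many patients RCT baseline may be the only usable one.

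**The case against.** A reader might infer that height and weight are reported only as raw values. The documents do not support that: 9.3.3 plans weight change, 2.2.2 promises change from both baselines, and Table 7 uses percent change. What is missing is standardisation for age and sex.

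The strongest counter-arguments are these.

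- **The tables are not wholly without contrast.** SAP Table 2 gives columns by former RCT arm and by protocol or annex enrolment. This stands in part. But all columns receive active drug in the extension, entrants are selected, and age is not adjusted for.
- **Follow-up may be short.** SAP section 1 says the extension is stopped prematurely and some planned assessments will not be done. SAP 9.5 says patients who enter will complete it per protocol and annex. The point about uncertain follow-up stands: the Day 365 and Day 729 rates may apply to few patients, and the number who will have a usable height series is unknown.
- **Nothing is lost.** All collected data are listed (SAP 6), SAP 6.1.8 allows further derivations, and section 1 allows labelled post-hoc work. The data are indeed recoverable, but the reference would then be chosen after the data are seen. The table shells are a separate document that was not available for this review.
- **Clinicians can report poor growth as an adverse event.** True for individual cases, but it depends on recognition and is no substitute for a summary of a primary component.
- **A z-score cannot attribute slowing to drug.** Correct. It is a reason to keep the display descriptive.

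**Conclusion.** The point holds as a gap in the planned displays. The unstandardised summaries and the age-blind 7% flag cannot show growth slower than expected for age. It is a cheap improvement to a descriptive analysis; no bias or loss of data has been shown.

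The 13.4%, 7.0% and 3.5% a year figures assume steady gain from OLE Day 1. A reader might take them as a measure of how many slow growers are missed. They are not: they describe the specificity of the upper flag, and the documents give no growth rates from which missed cases could be counted. The half-rate illustration rests wholly on assumed growth figures. The practical size depends on how long patients are actually followed, which SAP sections 1 and 9.5 leave unresolved.

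**What to change.** In SAP 9.3.3 and 9.3.5:

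- Derive age- and sex-specific weight and height z-scores from one growth reference named before analysis. Use age at the measurement date, since SAP 6.1.8.3 computes age at Visit 1 only.
- Summarise the observed z-score and its change from RCT baseline by visit, as a descriptive display. Give change from OLE baseline only where a Visit 1 value exists.
- Keep the 7% flag, and present the count with gains of 7% or more by the age groups already defined in SAP 7.3.

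The cost is SAP wording and a routine derivation from date of birth, sex, weight and height. It assumes that RCT-baseline height and weight are available, as SAP 2.2.2 presupposes. The downsides should be stated with the display: a general reference may not fit Rett syndrome, some heights are estimates (Protocol V2 9.2.6), and without a control a falling z-score cannot be attributed to the drug.

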9.3.4 Suicidality Assessment

The profound cognitive impairment of RTT patients is such that the Children's Columbia-Suicide Severity Rating Scale is not considered appropriate in this trial. Instead, suicidality will be assessed by the investigator via a clinical interview with the caregiver.

Responses to the suicidality assessment will be summarized by visit.

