Appendix 3.8 Suicidality Assessment

An example of the suicidality assessment is shown below:

- *Has the child expressed any wish to be dead?*
- *Has the child made any suicide attempts?*
- *Has the child harmed herself/himself in any way or shown any nonsuicidal self-injurious behavior?*

Study Code: GWND19002
 EudraCT Number: 2019-001605-24
 Clinical Protocol V1 09Aug19

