Appendix 3.10 Caregiver Assessment of Rett Symptoms

An example of the Caregiver Assessment of Rett Symptoms is shown below:

For each question, please choose the number on the scale that best describes your child.
 Please choose your answers based on what you observed over the past 7 days (since the last time you completed the diary).

1. Based on what you observed over the past 7 days, how was your child’s condition overall?
- 0 1 2 3 4 5 6 7 8 9 10
- Poor Excellent

2. Based on what you observed over the past 7 days, how much of the time was your child’s **breathing pattern irregular** overall?
Please consider any episodes of irregular breathing, such as your child’s hyperventilation and breath holding.
- 0 1 2 3 4 5 6 7 8 9 10
- None of the Time All of the time

3. Based on what you observed over the past 7 days, how **constipated** was your child overall?
Please consider how often your child has had bowel movements, how hard it was to push, and the size and consistency.
- 0 1 2 3 4 5 6 7 8 9 10
- Not at all constipated Extremely constipated

4. Based on what you observed over the past 7 days, how much of the time did your child have **repetitive hand movements**?
Please consider hand movements such as wringing, tapping, rubbing, washing movements, and hand mouthing
- 0 1 2 3 4 5 6 7 8 9 10
- None of the time All of the time

Study Code: GWND19002
 EudraCT Number: 2019-001605-24
 Clinical Protocol V1 09Aug19

5. Based on what you observed over the past 7 days, overall, how much of the time did your child engage in **behavior that led to harm or potential harm to herself or others?**
Please consider any self-injurious behavior and behavior that led to physical harm or potential harm to the child herself or others.

0	1	2	3	4	5	6	7	8	9	10
None of the time									All of the time	

6. Based on what you observed over the past 7 days, overall, how **anxious or sad** was your child?
Please consider whether your child showed signs such as fidgeting, crying or screaming. Also consider whether she appeared sad, withdrawn, or irritable.

0	1	2	3	4	5	6	7	8	9	10
Not at all anxious/sad									Extremely anxious/sad	

7. Based on what you observed over the past 7 days, how difficult was it for your child to **communicate her needs?**
Please consider all forms of communication your child may use (including both verbal and nonverbal communication, such as gestures, eye pointing, and communication devices).

0	1	2	3	4	5	6	7	8	9	10

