4.1.1 Primary Endpoint

Safety:

The long-term safety profile of GWP42003-P will be assessed by evaluating changes in the following, relative to the prerandomization baseline of the RCT:

- AEs
- Clinical laboratory parameters
- Vital signs
- Physical examination procedures
- 12-lead ECG
- Effects on menstruation cycles
- Suicidality
- Change in growth and development by measurement of height, weight, IGF-1 levels, and Tanner Staging (for patients aged ≥ 7 years or earlier, if clinically indicated by the onset of menarche or other signs of precocious puberty)

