13.6.2.5.1 Suicidality

Suicidality assessment responses will be summarized and listed as appropriate.

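### Suicidality is defined as change from two baselines, but the only table the SAP plans is a by-visit summary, so no planned summary counts patients who newly answer yes

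*SAP*

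**What the plan says.** Protocol section 4.1.1 lists suicidality among the components of the primary safety endpoint, to be assessed by "evaluating changes in the following, relative to the prerandomization baseline of the RCT". SAP section 2.2.2 repeats the definition ("assessed by evaluating changes in the following, relative to the prerandomization baseline of the GWND18064 lead-in trial") and adds: "The same analyses will be performed compared to OLE baseline".

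The analysis text is thinner. Protocol section 13.6.2.5.1 says: "Suicidality assessment responses will be summarized and listed as appropriate". SAP section 9.3.4 says: "Responses to the suicidality assessment will be summarized by visit". Neither describes a change from baseline, a shift table or a rule for a treatment-emergent response. SAP section 9.5, which records departures from the protocol analysis, mentions only the added OLE baseline.

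The questions themselves appear only in Appendix 3.8 of protocol version 1, where they are labelled an example. There are three: a wish to be dead, suicide attempts, and a third that reads "Has the child harmed herself/himself in any way or shown any nonsuicidal self-injurious behavior". None has a look-back period. Version 2, to which the SAP is written, describes only an interview with the caregiver.

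**The concern.** The endpoint asks whether suicidality or self-injury changes after baseline. A by-visit frequency table answers a different question: how many patients are positive at each visit. The two can diverge widely when the behaviour is common before treatment.

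For the third question that is plausible. The Caregiver Assessment of Rett Symptoms (version 1, Appendix 3.10, item 5) follows self-injury as part of the disease: "Please consider any self-injurious behavior and behavior that led to physical harm or potential harm to the child herself or others". A patient with the same self-injury at baseline and throughout adds to each visit total exactly as a patient with new self-injury does. One new case offset by one resolved case leaves the total unchanged. At stake is whether the report can state, from a planned table, the number of patients in whom the behaviour appeared after baseline.

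**Working it through.** The plan gives no rate, power or sample-size figure for suicidality, so there is no figure to reproduce. The check compares texts and then asks what by-visit totals can reveal.

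**1. How the SAP treats comparable safety data**

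| Component | Baseline comparison planned |
|---|---|
| Laboratory data (9.2.1) | Change from both baselines, and shift tables |
| Transaminases (9.2.1) | Treatment-emergent rule: criterion not met at baseline, met later |
| Vital signs (9.3.1), ECG (9.3.2) | Change from both baselines |
| Tanner stage (9.3.5), also categorical | Shift table |
| Suicidality (9.3.4) | None named |

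**2. What visit totals allow**

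Let N patients have a response at both times, with b yes at baseline and v yes at a visit. Let d be the number who are yes at both. New yes answers number v − d, and d lies between max(0, b + v − N) and min(b, v). Hence:

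- fewest new cases = max(0, v − b)
- most new cases = min(v, N − b)

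The planned enrolment of about 252 is from protocol section 13.1. The yes rates are assumptions, because the documents give none: 5% of 252 is 12.6 (13), 20% is 50.4 (50), 25% is 63 and 40% is 100.8 (101).

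| N | Yes at baseline | Yes at visit | New cases that fit |
|---|---|---|---|
| 252 | 13 | 13 | 0 to 13 |
| 252 | 50 | 50 | 0 to 50 |
| 252 | 50 | 63 | 13 to 63 |
| 252 | 101 | 101 | 0 to 101 |
| 20 | 4 | 4 | 0 to 4 |

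A baseline row in the table does not remove this range; b is already used in the formula. Only a per-patient cross-tabulation gives the number itself.

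**3. Denominator**

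SAP section 4.1 uses the whole study population as the default denominator, and section 9.3.4 does not override it. SAP section 1 says that the extension is stopping early and that some planned assessments will not take place. Suppose half of 252 patients have left (an assumption) and 25 of the remaining 126 answer yes. The rate among those assessed is 25/126 = 19.8%, the same as 50/252 before. The default percentage is 25/252 = 9.9%. The fall is attrition, not improvement.

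**4. Which baseline answers which question**

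SAP Table 2 separates patients by RCT treatment. For patients on GWP42003-P in the RCT, only the RCT baseline precedes drug. For patients on placebo, a shift from RCT baseline would also count behaviour that began on placebo; the OLE baseline is the last point before drug. Both comparisons, by RCT group, are therefore needed.

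The OLE baseline has a gap. SAP section 6.1.2 takes it from OLE Visit 1. Under footnote g of the schedule of assessments, suicidality is required at that visit only when it is not on the day of RCT Visit 9, and same-day entry is the recommended route (protocol section 4.1). For same-day entrants the SAP states no rule for carrying the RCT Visit 9 response forward.

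**The case against.** The strongest reply is that the information is not lost. SAP section 6 lists all collected data by patient in time order, and the protocol also lists suicidality responses. SAP Table 3 labels RCT Baseline and OLE Baseline as visits for all tables and listings, so the by-visit table can carry baseline rows. With an unchanged rate, those rows would show stability, not a false signal. New or worsening behaviour also qualifies as an adverse event under protocol section 12.1.1 and would appear in the TEAE tables. SAP section 8.5.4 summarises every item of the caregiver scale, including the harm item, as change from both baselines. The trial is descriptive, and the table shells are a separate document that is not available here.

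Most of this stands, and it limits the point. A reader might infer that existing Rett behaviour can never be told from new events on drug. The documents do not support that: where a baseline response exists, the listings separate the two. A reader might also infer that the three answers are pooled. Nothing says so, and only the third question mixes concepts. Its wording comes from a version 1 example, so the wording in use under version 2 cannot be confirmed.

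What remains is that listings, adverse events and a caregiver score are related evidence. None is a planned summary of the change that section 2.2.2 promises for this component.

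**Conclusion.** The SAP's analysis of suicidality does not deliver the endpoint as the SAP defines it. The mismatch rests on sections 2.2.2 and 9.3.4 alone and does not depend on how the third question is worded. In size, visit totals of 50 and 50 among 252 leave the number of new cases anywhere from 0 to 50. At the assumed rates of 5% and 40%, the ranges are 0 to 13 and 0 to 101.

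These figures illustrate; the true baseline rates are unknown, and the number enrolled may be well below 252. The point also assumes that baseline responses were recorded in the RCT, whose protocol is not among the documents.

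This is a missing summary in a descriptive trial, recoverable patient by patient, and not a loss of safety data. It is worth correcting because it concerns a component of the primary endpoint and the SAP already uses the needed method for Tanner stage.

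**What to change.** In SAP section 9.3.4:

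- Keep the by-visit table.
- For each question, add a No/Yes shift table from RCT baseline, and another from OLE baseline, to any assessment after Day 1. Present both by RCT treatment group, with the count of new yes answers among patients who were no at that baseline.
- State that the RCT Visit 9 response serves as OLE baseline for patients who enter on the same day. Footnote g implies that the assessment is made at that visit.
- Show the wish to be dead and suicide attempts apart from self-injury.

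The cost is a few extra tables from data already collected. New-onset counts for self-injury need a caution in the text: one baseline assessment is set against up to ten later ones (Visits 4 to 10, 12, 14 and 15). With no look-back period in the example questions, intermittent behaviour can appear as new onset.
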